2.1.2. Secondary Objectives

The secondary objectives include:

- To evaluate the efficacy of AD109 compared to R-oxybutynin alone as measured by HB(4%)
- To evaluate the efficacy of AD109 compared to atomoxetine alone as measured by HB(4%)
- To evaluate the efficacy of AD109 compared to the other 3 study treatments as measured by the 4% definition for hypopneas (AHI).
- To evaluate the efficacy of AD109 compared to the other 3 study treatments as measured by the 4% definition of oxygen desaturation index (ODI).
- To evaluate the efficacy of AD109 compared to the other 3 study treatments as measured by total time with $\text{SaO}_2 < 90\%$.
- To evaluate the efficacy of AD109 compared to the other 3 study treatments on the proportion of participants with $\geq 50\%$ reduction in AHI, HB and ODI.

2.1.3. Exploratory Objective

The exploratory objectives are to evaluate the effects of AD109 compared to the other 3 study treatments on:

- Snoring index
- Sleep stages distribution and percentage of time in the various sleep stages
- Arousal index
- Fraction of hypopneas

- Alternative measures of AHI, ODI and HB

An additional exploratory objective is to evaluate the effects of AD109 compared to the other study treatments in the subgroup of participants meeting “moderate collapsibility” polysomnography (PSG) criteria at baseline (PSG-0).

2.2. Endpoints

2.2.1. Primary Endpoint

The primary efficacy endpoint is as follows:

- Change in $\log_{10}(\text{HB}[4\%] + 1)$, (scored in reference to AHI[4%]), AD109 vs. placebo

2.2.2. Secondary Endpoints

The secondary efficacy endpoints are as follows:

- Change in $\log_{10}(\text{HB}[4\%] + 1)$, AD109 vs. R-oxybutynin alone
- Change in $\log_{10}(\text{HB}[4\%] + 1)$, AD109 vs. atomoxetine alone
- Change in AHI(4%), AD109 vs. other 3 study treatments
- Change in ODI(4%), AD109 vs. the other 3 study treatments
- Total time with $\text{SaO}_2 < 90\%$, PSG nights
- Proportion of participants with $\geq 50\%$ reduction, AHI(4%), HB(4%), and ODI(4%)

2.2.3. Exploratory Endpoints

The exploratory efficacy endpoints are as follows:

- PSG sleep and arousal parameters
 - Sleep stages distribution and percentage of time in the various sleep stages
 - Sleep Efficiency (SE)
 - Wake After Sleep Onset (WASO)
 - Number of Awakenings (NAW)
 - Sleep Onset Latency (SOL)
 - Percentage of total sleep time (TST) spent in sleep stage N1 (Stage N1%)
 - Percentage of TST spent in sleep stage N2 (Stage N2%)
 - Percentage of TST spent in sleep stage N3 (Stage N3%)
 - Percentage of TST spent in sleep stage R (Stage R%)
 - Snoring index
 - Arousal indices (respiratory and spontaneous)
 - Fraction of hypopneas

- Alternate measures of AHI, ODI and HB
 - AHI(4%) in non-rapid eye movement (NREM) sleep
 - AHI(4%) in rapid eye movement (REM) sleep
 - AHI(4%) adjusted for position
 - AHI(3% or arousal)
 - HB(3% or arousal)
 - HB(Total)
 - ODI(3%)
- Subgroup analyses of efficacy endpoints in participants meeting “moderate collapsibility” criteria (AHI[4%] 10 to <20, or AHI[4%] ≥20 if any one of the following are met: F_{hypopnea} of >90% OR mean oxygen desaturation of obstructive events of ≤4% OR F_{hypopnea} of 50 to 90% and mean oxygen desaturation of 4 to 8%) at baseline (PSG-0).

2.2.4. Safety Endpoints

The safety endpoints are as follows:

- Physical exam, vital signs, clinical laboratory assessment
- Spontaneous adverse events, including the post-dosing period
- Digit Symbol Substitution Test (DSST)
- PSG parameters:
 - Total sleep time (TST)
 - Heart rate (HR)
 - Total time with SaO₂<90%

3. INVESTIGATIONAL PLAN

3.1. Study Design

Study APC-003 is a double-blind, placebo-controlled, 4-period, single-dose crossover study designed to compare the efficacy of AD109 to placebo and the individual components of AD109 (atomoxetine and R-oxybutynin).

[figure not shown]
A total of 58 participants will be enrolled. Patients who meet all enrollment criteria will be randomized to receive the following experimental treatments, one treatment on each of 4 PSG nights:

- A: Atomoxetine 75 mg + R-oxybutynin 2.5 mg (AD109)
- B: Atomoxetine 75 mg
- C: R-oxybutynin 2.5 mg
- D: Placebo

Dosing of the study treatment will occur immediately prior to lights out. Each morning following PSG exams in the crossover period the DSST will be administered.

Each PSG night is followed by a 1-week washout period. Adverse event (AE) and serious adverse event (SAE) information is recorded at each study visit and by telephone contact with participants during each washout period and at the end of the final washout period. Overall study duration will be up to 10 weeks (see Figure 1).

Figure 1: Overview of Study Design

PSG = polysomnography

3.2. Treatment

Study treatment is defined as any investigational treatment(s), marketed product(s), placebo, or medical device(s) intended to be administered to a study participant according to the study protocol.

Two capsules are taken each night of drug treatment, either:

- 1 capsule of atomoxetine 75 mg + 1 capsule of R-oxybutynin 2.5 mg
- 1 capsule of atomoxetine 75 mg and 1 capsule of placebo
- 1 capsule of R-oxybutynin 2.5 mg and 1 capsule of placebo
- 2 capsules of placebo

Study medication is taken immediately prior to lights out.

3.2.1. Randomization Scheme and Treatment Arm Assignment

The randomization scheme will allocate participants to one of the following 24 treatment sequences: ABCD, ABDC, ACBD, ACDB, ADBC, ADCB, BACD, BADC, BCAD, BCDA, BDAC, BDCA, CABD, CADB, CBAD, CBDA, CDAB, CDBA, DABC, DACB, DBAC, DBCA, DCAB, DCBA (using treatments A, B, C, and D as defined in Section 3.1).

Participants who withdraw from the study will not be replaced.

3.2.2. Blinding

The investigator, study personnel and participant will be blinded to the identity of the study drug in all treatment periods. The CRO staff dealing with blinded site study staff will also be blinded. The Sponsor, Medical Monitor, CRO's Drug Safety and Pharmacovigilance staff, as well as site personnel required for drug administration will also be blinded. The centralized PSG technologists will be blinded to treatment assignment.

The CTI unblinded statistician who reviews the production randomization list will be unblinded to the treatment sequence a participant receives; however, this individual will not have access to study data prior to study completion. The investigational pharmacist and/or the study coordinator, depending on the site, will be unblinded to treatment assignment for the purposes of preparing, controlling, dispensing study product and documenting accountability of study product.

3.2.3. Dosing Schedule

There are 4 randomized crossover PSG nights. Each PSG night is followed by a 1-week washout period. Dosing of the study treatment will occur immediately prior to lights out.

3.2.4. Study Treatment Compliance

Only participants enrolled in the study treatments and only authorized site staff may supply or administer study treatments.

After receiving Sponsor approval in writing, sites are responsible for returning all unused or partially used study treatment to the Sponsor or designated third party or for preparing the study treatment for destruction via incineration. Unused study drug will be counted and recorded by study personnel to assess study treatment compliance.

4. GENERAL CONSIDERATIONS FOR DATA ANALYSIS

In general, continuous variables will be summarized by presenting the sample size (N), number of participants with available data (n), mean, standard deviation (SD), median, minimum, and maximum. In summaries of change from baseline safety variables, only participants with both baseline and post baseline data will be included. Categorical variables will be summarized by presenting the number and percentage of participants within each category. Calculation of percentages will exclude missing data as a category. Where appropriate, descriptive statistics may be presented with 95% confidence intervals (CIs).

All tabulations will be based on pooled data across centers.

The data analyses will be performed using SAS for Windows, version 9.4 or higher (SAS, Cary, NC), except where other software may be deemed more appropriate.

CTI Clinical Trial and Consulting Services (Covington, KY) will perform the efficacy and safety analyses. Apnimed, Inc., will perform subgroup analyses of efficacy endpoints in participants meeting "moderate collapsibility" criteria described in Section 2.2.3. Any changes to the analyses that are not included in this SAP will be documented in the clinical study report (CSR).

4.1. Data Quality Assurance

Once all the source verification is complete, all queries are resolved, and the database has been

updated appropriately, the database will be locked and made available to CTI Biostatistics for final analysis.

Data may be made available to CTI Biostatistics for programming purposes prior to database lock at a time when source verification and query resolution is ongoing.

All SAS programs used to create analysis data sets, tables, and listings will be independently programmed by two individuals. The independent SAS outputs produced will be compared, and the SAS programs will be updated until the outputs match.

4.2. Analysis Sets

4.2.1. Enrolled Set

The Enrolled Set is defined as all participants who signed the informed consent form (ICF) (including screening failures).

4.2.2. Modified Intent-To-Treat Analysis (mITT) Set

The mITT Set comprises all participants who are randomized, take at least 1 dose of any of the study treatments, and have at least 1 measurement on the primary endpoint.

Participants will be analyzed for efficacy according to the randomly assigned treatment for each period.

4.2.3. Safety Set

The Safety Set consists of all participants who are randomized and receive at least 1 dose of any of the study treatments. Participants will be analyzed for safety based on the treatment received for each period. Treatment received is defined as the actual treatment taken during each period.

4.2.4. Per Protocol (PP) Set

The PP Set consists of all participants without any major protocol violations that could influence efficacy assessment. Participants in this set will be analyzed according to the treatment they received for each period. Treatment received is defined as the actual treatment taken during each period.

4.3. Assessment Windows

Data will be summarized by the eCRF (Study Visit) in which it was collected as long as the data is within the windows specified.

4.4. Handling of Dropouts or Missing Data

Missing data will remain missing. No imputation of missing data will be performed.

4.4.1. PSG Parameters

The criteria for use of PSG data will be as follows:

- When TST is < 120 minutes, only TST, time in bed, Stage N1%, Stage N2%, Stage N3%, and Stage R% will be reported. All other PSG indices will be excluded.

- Any AHI and HB parameters during REM will be reported only when the time spent in REM is > 5 minutes.
- Any AHI and ODI parameters in supine position will be reported only when the time spent supine is > 5 minutes.

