## 7.1.1 Polysomnography

- Methods: Standard overnight PSG recording and data interpretation will be performed in accordance with the American Academy of Sleep Medicine (AASM) scoring manual.
   Participants will be instrumented with standard PSG electrodes. Time of lights out will be established according to the participants' habitual schedule and kept constant across the PSG study nights. The participants will be given 8 hours of time-in bed.
- Scoring: All PSG studies (including screening PSG) will be scored by centralized PSG technologists, blinded to treatment assignment. Scoring will be conducted according to the American Academy of Sleep Medicine manual scoring criteria.

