## 7.2 Safety Assessments

- Planned time points for all safety assessments are provided in the SoA.
- Safety monitoring will be guided by the established safety profiles of atomoxetine and
  oxybutynin, and by Phase 1 and 2 safety data for the combination. Safety assessments will
  include physical examinations, measurement of vital signs, monitoring and recording of AEs,
  SAEs, and pregnancies, recording of study or treatment discontinuations. Effects on OSA and
  sleep parameters (e.g., sleep time and sleep stages) will also be monitored by PSG.
- Adverse events of special interest include effects on urine outflow, as both atomoxetine and oxybutynin are associated with urinary retention. Effects of atomoxetine on heart rate and blood pressure are expected to be modest, as indicated by the initial data described above, and will also be monitored. Participants with serious cardiac abnormalities will be excluded from the study. Suicidal ideation in children and adolescents is a boxed warning for atomoxetine; however, analysis in adult patients, the target population for the proposed OSA study, did not reveal an increased risk of suicidal ideation or behavior in association with atomoxetine. Daytime sleepiness is both a potential safety outcome and efficacy outcome in OSA. Both atomoxetine and oxybutynin may be associated with somnolence, and oxybutynin is additionally associated with anticholinergic CNS effects such as memory difficulty.

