6.3. Exploratory Efficacy Analyses

Descriptive statistics for the reported value and change from baseline by study treatment will be reported for sleep stages distribution and percentage of time in the various sleep stages (SE, WASO, NAW, SOL, Stage N1%, Stage N2%, Stage N3%, Stage R%). A 95% confidence interval will be included for the change from baseline.

Snoring index, arousal indices (respiratory and spontaneous), fraction of hypopneas (see below) and alternate measures of AHI, ODI, and HB (AHI[4%]: in NREM sleep, in REM sleep, AHI adjusted for position [see below]; AHI[3% or arousal]; HB[3% or arousal]; HB[Total]; ODI[3%]) and will have results provided similar to Section 6.1 (including the model of change from baseline and the descriptive statistics).

Additional clarifying details for the analysis of some of these endpoints is as follows:

- Fraction of hypopneas will be calculated by using the number of hypopneas divided by the total number of apneas plus hypopneas.
- AHI adjusted for position: An additional covariate of % time supine (%TS) will be added to the repeated measures model for AHI(4%).

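### SAP 4.4.1 drops sleep efficiency, WASO, awakenings and sleep-onset latency on nights with under 120 minutes of sleep, which biases mean sleep efficiency upward for any treatment that causes such nights

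*SAP*

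**What the plan says.** SAP 4.4.1 sets a reporting rule for nights with little sleep: "When TST is < 120 minutes, only TST, time in bed, Stage N1%, Stage N2%, Stage N3%, and Stage R% will be reported". The next sentence adds: "All other PSG indices will be excluded". SAP 4.4 closes the other route by which values could return: "Missing data will remain missing. No imputation of missing data will be performed".

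SAP 2.2.3 lists SE, WASO, NAW and SOL as exploratory endpoints. SAP 6.3 names the set to be summarised ("SE, WASO, NAW, SOL, Stage N1%, Stage N2%, Stage N3%, Stage R"), with descriptive statistics by treatment and a 95% confidence interval for change from baseline. Neither section makes an exception to the 120-minute rule.

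On the length of the night, Protocol 7.1.1 says: "The participants will be given 8 hours of time-in bed". On safety, Protocol 7.2 says that "sleep parameters (e.g., sleep time and sleep stages) will also be monitored by PSG". SAP 2.2.4 and 7.5 keep TST as a polysomnographic safety parameter, summarised by treatment.

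**The concern.** A minimum amount of sleep is a natural condition for rates per hour of sleep, which become erratic when the denominator is small. SE, WASO, NAW and SOL are not rates of that kind and can be scored on a short night. The SAP gives no reason for dropping them. It retains TST and time in bed, from which SE is formed, but not SE. It also retains the stage percentages, whose denominator is the short TST itself.

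For SE, the exclusion depends on the value of the endpoint. Dosing is immediately before lights out, so the recorded night is the exposed night. If a treatment sometimes prevents sleep, those nights leave its SE summary and the remaining mean looks better than the treatment's actual record. What is at stake is the accuracy of the exploratory sleep tables and their agreement with the TST safety table. The primary and secondary efficacy tests are not affected.

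**Working it through.** The documents state no figure for the effect of this rule, so there is none to reproduce.

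**Inputs from the documents**
- Cut-off: TST below 120 min (SAP 4.4.1).
- Time in bed: 8 h = 480 min (Protocol 7.1.1).
- Participants: 58 (SAP 3.1), with discontinuation below 20% (SAP 9). At the 20% limit, 58 × 0.8 = 46.4, or about 46 completers.

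**Assumed definitions** (the SAP does not spell them out)
- SE = TST / time in bed.
- SOL + WASO = time in bed − TST, with WASO counted up to lights on.

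**Step 1: what the cut-off means**
- SE: 120 / 480 = 25%. With a shorter time in bed it is 120 / 450 = 26.7% or 120 / 420 = 28.6%.
- Wake time: 480 − 120 = 360 min, so SOL + WASO exceeds 360 min on every dropped night.

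**Step 2: endpoint by endpoint, at a fixed time in bed**
- SE: every dropped value is below 25% and every kept value is 25% or more. The worst values are removed.
- SOL + WASO: every dropped sum is above 360 min and every kept sum is 360 min or less. The largest sums are removed.
- SOL or WASO singly: not separated. A night with TST 110 and SOL 20 has WASO 480 − 110 − 20 = 350, and its ordinary SOL is dropped. A night with TST 150 and SOL 300 has WASO 480 − 150 − 300 = 30, and its extreme SOL is kept.
- NAW: the cut-off implies nothing. One long awakening gives a low count on a dropped night, and a long fragmented night can give a high count and is kept.

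The ordering in SE is exact for the recorded value. Change from baseline also depends on each participant's baseline, so the same direction is expected there but not guaranteed.

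**Step 3: illustrative size (assumed values)**
Let N be the nights recorded on a treatment and k the number dropped. Then:
- overstatement of mean SE = (k/N) × (mean SE of kept nights − mean SE of dropped nights);
- understatement of mean wake time = 480 min × the same quantity as a fraction.

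Assume that kept nights average SE 80% and dropped nights 10% or 20%.

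| N | k | Dropped SE | Mean SE, all nights | SE reported | SE too high by (points) | Wake too low by (min) |
|---|---|---|---|---|---|---|
| 58 | 0 | – | 80.0 | 80 | 0 | 0 |
| 58 | 1 | 20% | 79.0 | 80 | 1.0 | 5.0 |
| 58 | 3 | 20% | 76.9 | 80 | 3.1 | 14.9 |
| 58 | 5 | 10% | 74.0 | 80 | 6.0 | 29.0 |
| 46 | 1 | 20% | 78.7 | 80 | 1.3 | 6.3 |
| 46 | 5 | 10% | 72.4 | 80 | 7.6 | 36.5 |

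First non-zero row: (57 × 80 + 1 × 20) / 58 = 4580 / 58 = 78.97, and 80 − 78.97 = 1.03.

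**Step 4: agreement between tables**
Take the row with k = 3 of 58. Kept nights have TST 0.80 × 480 = 384 min and dropped nights 0.20 × 480 = 96 min. The TST table, which keeps all nights, averages (55 × 384 + 3 × 96) / 58 = 369.1 min, or 76.9% of 480. The SE table would show 80%.

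**The case against.** The strongest reply is that little is lost and nothing is concealed. TST is kept on every night and summarised by treatment with no cut-off (SAP 7.5). Every minute missing from the SE table is therefore present in the TST table, and SE can be recomputed from two retained quantities. SAP 4 shows both N and the number with data for continuous variables, so dropped nights appear as a smaller n for SE than for TST. SAP 7.5 also plans participant-level listings. The sleep parameters that Protocol 7.2 names as examples, sleep time and stages, are the ones the rule keeps. The four endpoints are exploratory, are summarised descriptively, and lie outside the testing sequence in SAP 4.5. The exclusions for insomnia history and for typical sleep under 5 hours (Protocol 5.2) should make such nights uncommon.

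All of that stands as a limit on impact. It does not justify the rule: screening on usual sleep does not rule out a response to study drug, and a reader of the SE table should not have to rebuild it from another one. Reading the word indices narrowly in the second sentence does not rescue the four measures either, because the first sentence already limits what is reported.

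A reader might infer three stronger claims that the documents do not support:
- That all four endpoints lose exactly their worst values. This is true of SE, true of SOL and WASO only as a sum, and does not follow for NAW.
- That a sleep-disrupting treatment would appear neutral for sleep. TST would still show the loss.
- That the dropped nights fall in one treatment only. The documents say nothing about their distribution. If all treatments lose them about equally, the comparison of means is little affected.

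**Conclusion.** The point holds as a limited one. As written, SAP 4.4.1 removes SE, WASO, NAW and SOL on nights with TST under 120 min, without a stated reason and without replacement. For any treatment that causes such nights, mean SE is biased upward and mean total wake time (SOL plus WASO) downward, and the SE and TST tables can disagree. This rests on SE being TST over time in bed, on a time in bed close to the planned 480 min, and on WASO running to lights on.

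The size is unknown because the documents give no frequency for these nights. On the assumed values above, with one to five dropped nights on a treatment, mean SE is too high by 1.0 to 7.6 points and mean wake time too low by about 5 to 37 min. With none, the bias is zero. No efficacy conclusion depends on these endpoints, so this is a cheap improvement to the SAP and not a threat to the trial's result.

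**What to change.** In the first bullet of SAP 4.4.1, add SE, WASO, NAW and SOL by name to the measures kept when TST is below 120 min, and leave the rest of the rule unchanged. In the SAP 6.3 tables, add a row giving the number of nights with TST below 120 min by treatment. It is worth stating how a night with no sleep at all is entered, since SOL and WASO have no natural value then.

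Naming the four is safer than redefining the exclusion as covering only rates per hour of sleep or per respiratory event. That wording would bring back total time with SaO2 below 90%, which is neither kind of measure. It is a secondary endpoint in the fixed testing sequence (SAP 2.2.2, 4.5 and 6.2.3). On a nearly sleepless night there is little sleep in which to desaturate, so its return could credit a sleep-disrupting treatment with better oxygenation. Respiratory and oximetry measures should stay excluded on these nights, as now.

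The cost is a sentence or two and one table row, with no new data and no change to the primary analysis. The downside is that a few extreme values will widen the standard deviations in the sleep tables.

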4.4.2. DSST Scores

A DSST total correct of 0 will be dropped from the repeated measures model.

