7. SAFETY ANALYSIS

Safety assessments will include measurement of adverse events (AEs) and serious AEs (SAEs).

The analyses will be descriptive and will be based on the Safety Set. The safety assessments will be summarized by the treatment the participant actually received within each period.

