7.4. DSST

A repeated measures model (see Section 4.7) will be used to model the natural log of total number of the correct symbol assignments¹ (log (total completed - total incorrect)) from the DSST.

Exponentiation of the model-based LS mean estimates of log values will be used to provide the following:

- Geometric mean of DSST by study treatment (AD109, placebo, R-oxybutynin, and atomoxetine), and
- Ratio of (geometric) mean of DSST between AD109 and the other three treatments (placebo, R-oxybutynin, and atomoxetine) with the 95% confidence intervals.

Descriptive statistics of DSST and a by-participant listing (with both raw values and natural log of total complete) will also be provided.

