7.5. PSG Parameters

PSG safety data will be summarized by presenting descriptive statistics of actual values and changes from baseline by treatment. PSG safety parameters include total sleep time, heart rate, and total time with $\text{SaO}_2 < 90\%$. A by-participant listing of PSG parameters (including baseline and efficacy parameters) will also be provided.

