9. SAMPLE SIZE AND POWER CALCULATIONS

A total of 58 patients will enter the 4-treatment crossover study. The study will have 80% power to detect a treatment difference at a two-sided 0.05 significance level, if the true difference between treatments on HB is at least -3.7 %min/h. This assumes that the within-participant

¹ In the case that the total correct is 0, the participant will be dropped from the model.

standard deviation is 9, estimated from Study APN-006, and that the discontinuation rate is less than 20%.

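### The SAP gives two conflicting rules for a DSST score of 0 (drop the record or drop the participant), and its 120-minute sleep rule makes no exception for heart rate in the PSG safety table

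*SAP*

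**What the plan says.** **DSST.** SAP 7.4 fits the repeated measures model of SAP 4.7 to the natural log of the number of correct symbols. Two rules cover a score of 0:

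- SAP 4.4.2: "A DSST total correct of 0 will be dropped from the repeated measures model".
- Footnote 1, attached to SAP 7.4 and printed at the foot of the page on which SAP 9 begins: "In the case that the total correct is 0, the participant will be dropped from the model".

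The general missing-data rule in SAP 4.4 is "Missing data will remain missing. No imputation of missing data will be performed". Outside the model, SAP 7.4 adds: "Descriptive statistics of DSST and a by-participant listing (with both raw values and natural log of total complete) will also be provided". The protocol has no rule for a zero.

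**PSG safety data.** When total sleep time (TST) is under 120 minutes, SAP 4.4.1 lets only TST, time in bed and the four sleep-stage percentages be reported, and continues: "All other PSG indices will be excluded". SAP 7.5 states that "PSG safety parameters include total sleep time, heart rate" and total time with SaO2 <90%. Neither section refers to the other, and the safety endpoint list in SAP 2.2.4 contains no exception.

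**The concern.** The two DSST rules apply to the same model but remove different units. Any zero therefore produces two possible data sets. SAP 4.1 has two people program each output independently and reconcile until they agree. A conflict of this kind could surface as a mismatch that is settled only once data are in hand. The wider rule also discards valid scores from the same person on other treatments.

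The PSG rule is a gap, not a contradiction. On a short night, two of the three parameters in the SAP 7.5 table drop out. What triggers the loss is TST, which is measured after dosing and is itself a safety endpoint. Protocol section 3 names PSG heart rate and oximetry as safety endpoints without a minimum sleep time, and Protocol 7.2 says that effects of atomoxetine on heart rate will be monitored. The 12-lead ECG is scheduled only at V1, so the PSG recording matters for heart rate after dosing.

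**Working it through.** The documents give no figure on this point, so there is none to reproduce. The check is a count of what each rule removes.

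**Inputs.** 58 participants and one DSST after each of 4 crossover nights (SAP 3.1); discontinuation below 20% (SAP 9).

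**Records.** The total is 58 × 4 = 232. Let k participants have one zero each. Dropping the score keeps 232 − k, and dropping the participant keeps 232 − 4k.

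| k | Score dropped | Participant dropped |
|---|---|---|
| 1 | 231 | 228 |
| 2 | 230 | 224 |
| 3 | 229 | 220 |

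At the lower end, 58 × 0.20 = 11.6, so at most 11 discontinue and 47 remain. Then 47 × 4 = 188, and one zero leaves 187 or 184.

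**Within-person AD109 contrasts.** Each participant supplies three: AD109 against placebo, R-oxybutynin and atomoxetine. They share one AD109 night, so they are not independent.

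- *Zero on a comparator night.* Dropping the score loses 1 contrast and dropping the participant loses 3. The excess is 2, which is 2/174 = 1.1% with 58 participants (58 × 3 = 174) or 2/141 = 1.4% with 47 (47 × 3 = 141).
- *Zero on the AD109 night.* Both rules lose all 3, so the excess is 0. The wider rule still removes three valid comparator scores from the treatment geometric means.

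**Is the wider drop needed?** No. ln(0) is undefined only for the zero record. SAP 4.4 leaves missing data missing, and the SAP 4.7 model can use the participant's other nights.

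**PSG rule.** Set side by side, SAP 4.4.1 permits TST on a short night, but neither heart rate nor time with SaO2 <90% is on its permitted list. The two excluded parameters behave differently:

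- *Heart rate.* If one short night differs from the rest by an assumed 5 to 20 bpm, including it moves that treatment's mean by 5/58 = 0.09 to 20/47 = 0.43 bpm. The 5 to 20 bpm is an assumption, not a figure from the documents.
- *Time with SaO2 <90%.* This is a total. At an unchanged desaturation fraction, 119 minutes of sleep accrues 119/450 = 26% to 119/360 = 33% of what a night of 360 to 450 minutes would. That range is assumed; Protocol 7.1.1 gives only 8 hours in bed. Including short nights could make short sleep look like better oxygenation.

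**The case against.** **The footnote may be loose wording.** SAP 4.4.2 is the dedicated data-handling section, and the footnote may mean only that participant's record. That is plausible, but as written the footnote removes the participant, and one sentence settles it.

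**A zero cannot stay in a log model.** This stands. A reader might infer that zeros vanish from the report, or that an extra model on the untransformed score is required. The documents do not support either. SAP 4 summarises continuous variables by "number of participants with available data (n), mean, standard deviation (SD), median, minimum, and maximum", and SAP 7 adds that "The safety assessments will be summarized by the treatment the participant actually received within each period". Zeros therefore remain visible by treatment, including in the minimum, and in the listing. A second model would be a preference, and it would estimate a difference instead of a ratio.

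**Heart rate may not be a PSG index.** This is open. The restriction to a closed list in SAP 4.4.1 and the label in SAP 7.5 favour exclusion, but confidence is medium. SAP 7.5 also promises a by-participant PSG listing. Because SAP 4.4.1 governs what is reported, it is unclear whether that listing would show the excluded values.

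**A threshold that treats all arms alike is defensible.** For time with SaO2 <90% this stands, given the 26% to 33% above. It has less force for heart rate, which is not a total that grows with sleep time.

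**Other heart-rate data exist.** Vital signs are taken on PSG nights after admission to the laboratory. A reader might infer that PSG is the only heart-rate source after dosing. The documents do not say whether those vital signs precede the dose, so that cannot be claimed.

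**Conclusion.** Both parts hold, and both are minor.

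The DSST rules conflict with high confidence. One zero makes a difference of three records (231 against 228 of 232), with two extra AD109 contrasts lost or none, depending on the night. The participant-level rule has no justification in the SAP.

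The PSG gap holds on the literal text with medium confidence. It matters for heart rate. Keeping short nights out of the summary of time with SaO2 <90% is acceptable if those nights are listed and counted.

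A reader might infer that these rules hide impairment or favour AD109. The documents do not support that. The numbers of zeros and short nights are not given and may be nil, and no direction of bias is shown. TST, adverse events and vital signs are kept, and the n in each summary shows how many values are missing. DSST and PSG heart rate lie outside the testing sequence in SAP 4.5. Time with SaO2 <90% is also a secondary efficacy endpoint, but the point concerns only its use as a safety parameter. No efficacy conclusion depends on this.

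**What to change.** Before unblinding:

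1. Delete the footnote to SAP 7.4, or reword it to match SAP 4.4.2, so that only the zero record leaves the log model. Report the number of zeros by treatment.
2. State in SAP 4.4.1 that the 120-minute rule governs efficacy indices and does not remove PSG heart rate from the SAP 7.5 summary and listing. Show heart rate with and without nights of TST under 120 minutes.
3. Report the number of such nights by treatment. Time with SaO2 <90% may stay out of the safety summary on those nights if they are listed and counted.

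The 120-minute rule for efficacy stays as it is. If unblinding has already taken place, the clinical study report should state which DSST rule was applied and how short nights were handled.

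The cost is a few SAP sentences, two counts and one additional heart-rate display, all from data already collected. The downside is that heart rate on a night with little sleep may not be comparable with other nights, which is why both versions are shown. A table note must say which nights each summary includes.
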